Sample Size:	A total of 160 subjects will be enrolled into the study.
Number of Sites:	Up to 28 clinical sites in the US
Study Population:	Subjects with unruptured, angiographically confirmed wide-neck (\geq 4 mm or a dome-to-neck ratio $<$ 2) intracranial aneurysms located at the bifurcation of the basilar artery, carotid terminus, MCA and ACOM arising from the parent vessel for the target aneurysm with a diameter of 2.0 mm to 4.5 mm will be eligible for the study.

Study Procedures:

The study evaluation time points include:

1. Screening/Baseline
2. Procedure
3. Hospital Discharge
4. 30 Day Follow-up (Clinic Visit)
5. 180 Day Follow-up (Clinic Visit)
6. 1 Year Follow-up (Clinic Visit and DSA)
7. 2 Year Follow-up (Telephone Call)
8. 3 Year Follow-up (Clinic Visit and DSA or MRA)
9. 4 Year Follow-up (Telephone Call)
10. 5 Year Follow-up (Clinic Visit and DSA or MRA)

Primary Safety Endpoint:

Composite of Neurological Death or Major Ipsilateral Stroke (in downstream territory) up to 1 year post-procedure:

- *Stroke is defined as rapidly developing clinical signs of focal (or global) disturbance of cerebral function lasting more than 24 hours with no apparent cause other than of vascular origin, including ischemic stroke and/or hemorrhagic stroke (i.e., intraparenchymal hemorrhage (IPH), subarachnoid hemorrhage (SAH), subdural hemorrhage (SDH), epidural hemorrhage (EDH)). [Hatano 1976].*
- *Major Stroke is defined as stroke with symptoms persisting for more than 24 hours AND a sudden increase in the NIHSS of the subject by ≥ 4 .*

Primary Effectiveness Endpoint:

Complete Occlusion:

Rate of complete aneurysm occlusion (Raymond I) without significant parent artery stenosis ($> 50\%$ stenosis) or prior retreatment at 1 year post-procedure.

Secondary Effectiveness Endpoints:

- Technical Success is defined as successful implantation of device— physician able to access target aneurysm, deploy PulseRider® device at the neck of aneurysm and device was detached successfully
- Ability to retain embolic coils within aneurysm immediately post-procedure (as evaluated by the core lab)
- Complete aneurysm occlusion at 3 years and 5 years
- Adequate aneurysm occlusion (defined as Raymond I and II combined) at 1 year, 3 years and 5 years

- The percentage of target aneurysms that are retreated through 1 year, 3 years and 5 years
- The percentage of subjects with significant stenosis defined as $> 50\%$ at implant site at 1 year, 3 years and 5 years.

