1.1. Background Information

An intracranial aneurysm is an abnormal dilatation that occurs in an artery as the result of a weakening in the wall of the vessel. This balloon like outpouching fills with blood and may enlarge over time; most commonly this occurs at the junctions or bifurcations of major arteries. As the aneurysm increases in size, the vessel wall becomes thinner and more fragile and is at risk of rupture. Many intracranial aneurysms remain silent and are never diagnosed unless they rupture resulting in a subarachnoid hemorrhage (SAH) or gradually enlarge over time and exert pressure on the surrounding brain tissue resulting in a variety of morbidities. These aneurysms are typically diagnosed because of the associated symptoms e.g. cranial neuropathies, visual disturbances, etc. Asymptomatic, unruptured aneurysms may also be discovered incidentally as a result of some other suspected pathology e.g. migraine headache, dizziness, etc. that requires diagnostic imagining. The most common presentation of an intracranial aneurysm however, is SAH, which is a life-threatening event. Even with prompt medical attention there is a high incidence of morbidity and mortality. Between 40% and 67% of ruptured aneurysms result in death within one month and 10% to 20% of the survivors have major morbidities [Woo 2002]. The primary goal of surgery or endovascular treatment of any aneurysm is to reduce the risk of initial or recurrent subarachnoid hemorrhage by excluding the lesion from the cerebral circulation.

Risk factors for the formation of aneurysms include a family history, various inherited disorders such as polycystic kidney disease, age greater than 50 years, female gender, hypertension, trauma, atherosclerosis, abnormal flow at a vessel bifurcation and current cigarette smoking [Vega 2002]. A strong female predilection has been observed in patients with aneurysms, especially those with multiple aneurysms. There are other rare causes of aneurysms such as infections of the artery wall and drug abuse, especially cocaine, which can cause the artery walls to become inflamed and weakened.

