3.2. Study Endpoints

3.2.1. Primary Endpoint - Safety

Composite of Neurological Death or Major Ipsilateral Stroke (in downstream territory) up to 1 year post-procedure:

Stroke is defined as rapidly developing clinical signs of focal (or global) disturbance of cerebral function lasting more than 24 hours with no apparent cause other than of vascular origin, including ischemic stroke and/or hemorrhagic stroke (i.e., intraparenchymal hemorrhage (IPH), subarachnoid hemorrhage (SAH), subdural hemorrhage (SDH), epidural hemorrhage (EDH)) [Hatano 1976].

Major Stroke is defined as stroke with symptoms persisting for more than 24 hours AND a sudden increase in the NIHSS of the subject by > 4 .

Minor Stroke is defined as stroke with symptoms persisting for more than 24 hours and a sudden increase in the NIHSS of the subject by 1-3.

TIA is defined as stroke symptoms resolving within ≤ 24 hours.

This endpoint will be adjudicated by the independent Clinical Events Committee (CEC).

[figure not shown]

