3.2.2. Primary Endpoint - Effectiveness

Complete Occlusion:

Rate of complete aneurysm occlusion (Raymond I) without significant parent artery stenosis ($> 50\%$ stenosis) or prior retreatment at 1 year post-procedure.

The aneurysm occlusion and parent artery stenosis assessments in this endpoint will be evaluated by the independent core laboratory. Retreatment will be reported by the site.

Figure 3.2.2A Raymond Scale [Roy 2001]

- **Class I: Complete** = Complete obliteration
- **Class II: Residual Neck** = Persistence of any portion of the original defect of the arterial wall but without opacification of the aneurysmal sac
- **Class III: Residual Aneurysm** = any opacification of the aneurysm sac

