3.2.4. Additional Endpoints

- The percentage of target aneurysm rupture up to 1 year, 3 years and 5 years. This endpoint will be evaluated by the independent core laboratory.
- No migration (defined as $\leq 2\text{mm}$) of the device at 1 year, 3 years and 5 years. This endpoint will be evaluated by the independent core laboratory.

4. Study Population

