10.3.4. Primary Endpoint Analyses

Primary Safety Endpoint

The primary safety endpoint analysis will be conducted on the mITT analysis set.

If a subject experienced a death due to neurological causes or a major ipsilateral stroke in downstream territory within a year post-procedure then subject will be deemed a failure on the endpoint. If a subject completed the 1 year follow up and did not experience any such event then subject will be deemed a success on the endpoint. If a subject did not complete the 1 year follow up and did not experience such event then the subject will be imputed with a multiple imputation method that will make use of the similarities between the subject's demographic, procedural, and aneurysm characteristics with those of the subjects with a non-missing endpoint (those who either experienced an event and those who completed the study without experiencing an event). The imputation method will also account for the length of time between the procedure and the last time the subject was seen. The longer that time period is, the less likely the subject will be imputed with an event.

Subjects for whom implantation of the PulseRider was attempted but not successful will be followed up to a year. Any safety events which occur due to attempted implant or from retreatment, and which meet the primary safety endpoint definition will count as failures in the analysis. If such a subject is lost to follow-up then subject will be imputed with data based on other subjects for whom the implantation was not successful but who were not lost to follow-up.

The multiple imputation method results in a large collection of imputed datasets. The proportion of primary endpoint events and its variance is computed for each dataset. Within and between imputation variances are then combined according to Rubin's method [Rubin 1996] in order to produce a single variance estimate for the proportion of events.

The endpoint will be considered successful if the upper bound of the 2-sided 95% normal approximation based confidence interval for the rate of events is less than a performance goal of 15%.

Primary Effectiveness Endpoint

The primary effectiveness endpoint analysis will be conducted on the PP analysis set.

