Success on this endpoint is defined as complete aneurysm occlusion (Raymond I) without retreatment or significant parent artery stenosis (> 50% stenosis) at 1 year post-procedure. If the 1 year imaging is not available and if the subject did not experience a retreatment then the subject will be imputed using an imputation method that will make use of the subject's own past occlusion and stenosis evaluations if available and the similarities between the subject's demographic, procedural, and aneurysm characteristics with those of the subjects with a non-missing endpoint.

The multiple imputation method results in a large collection of imputed datasets. The proportion of complete aneurysm occlusion and its variance is computed for each dataset. Within and between imputation variances are then combined according to Rubin's method in order to produce a single variance estimate for the proportion of complete aneurysm occlusion.

The endpoint will be considered successful if the lower bound of the 2-sided 95% normal approximation based confidence interval for the rate is greater than a performance goal of 46.3%.

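### Rupture of the treated aneurysm is not itself a failure on either primary endpoint, and a subject who ruptures before the 1-year image can be imputed as an effectiveness success

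*Combined protocol and SAP*

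**What the plan says.** **Effectiveness.** Section 10.3.4 states: "Success on this endpoint is defined as complete aneurysm occlusion (Raymond I) without retreatment or significant parent artery stenosis", assessed at 1 year with stenosis meaning more than 50%. Section 3.2.2 has the same three parts and words the retreatment part as "or prior retreatment at 1 year post-procedure". If the 1-year image is missing and there was no retreatment, 10.3.4 sends the subject to multiple imputation. The imputation draws on the subject's own past occlusion and stenosis readings where they exist, and on similar subjects.

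**Safety.** Section 10.3.4 counts a failure as follows: "If a subject experienced a death due to neurological causes or a major ipsilateral stroke in downstream territory within a year post-procedure". Subarachnoid hemorrhage falls within the stroke definition in 3.2.1, but the stroke must also be major. An NIHSS rise of 1 to 3 is a minor stroke there and is not a primary safety event.

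**Rupture.** Section 3.2.4 lists it as an additional endpoint: "The percentage of target aneurysm rupture up to 1 year, 3 years and 5 years". It is assigned to the core laboratory (3.2.4, 10.1.3, 10.3.6) and analysed in the per-protocol set on observed data, with no hypothesis or performance goal.

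**Purpose of treatment.** Section 1.1 states: "The primary goal of surgery or endovascular treatment of any aneurysm is to reduce the risk of initial or recurrent subarachnoid hemorrhage". The sentence goes on to name exclusion of the lesion from the circulation as the means.

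**The concern.** Complete occlusion at 1 year is an anatomical stand-in for protection from bleeding. A subject whose treated aneurysm has bled in the meantime has lost that protection, whatever the later image shows. Such a subject should not add to the numerator of the effectiveness claim.

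The imputation rule is the sharper part of the problem. Retreatment is the only event that makes a subject without a 1-year image a known failure. Death from rupture does not. A subject who dies of target-aneurysm rupture at month 8 after a good image at month 6 would have effectiveness filled in partly from that good image. Here the rule as written gives a wrong answer; it does not merely leave a detail open.

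**Working it through.** **Step 1: apply the two rules to each kind of post-procedure rupture** (per-protocol subject, no parent artery stenosis >50%).

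| Course after rupture | Safety | Effectiveness |
|---|---|---|
| Non-fatal, below major-stroke threshold, not retreated, Raymond I at 1 year | success | success |
| Same, but retreated | success | failure |
| Same, not retreated, Raymond II or III at 1 year | success | failure |
| Same, not retreated, no 1-year image | success if 1-year follow-up is completed, otherwise imputed | imputed, can be success |
| Major stroke, judged ipsilateral and downstream, not retreated, Raymond I at 1 year | failure | success |
| Neurological death before the 1-year image, not retreated | failure | imputed, can be success |

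The first row is success on both endpoints. In the fourth and sixth rows effectiveness is left to imputation although the outcome is known. The second and third rows show that effectiveness already catches part of the problem.

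**Step 2: the threshold that separates the rows is not settled.** The Protocol Summary defines major stroke by "a sudden increase in the NIHSS of the subject by ≥ 4". Section 3.2.1 has "AND a sudden increase in the NIHSS of the subject by > 4". With minor stroke at 1 to 3, a rise of exactly 4 has no class under 3.2.1. The derivation of the safety goal in 10.1.1 uses 4 or more. These passages must be reconciled.

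**Step 3: reproduce the plan's effectiveness power.** Inputs from 10.2: 160 subjects, 10% attrition, goal 46.3%, expected rate 58.8%. Two-sided alpha of 0.05 is from 10.1.5.

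- n = 160 × 0.9 = 144.
- Standard error under the goal: √(0.463 × 0.537 / 144) = 0.04155. Under the expected rate: √(0.588 × 0.412 / 144) = 0.04102.
- z = (0.125 − 1.96 × 0.04155) / 0.04102 = 1.06, so power is 85.6%. The stated 85% reproduces.

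**Step 4: the pass mark with 144 complete subjects.** Lower bound = p − 1.96 × √(p(1 − p)/144).

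- 79/144 = 54.9%: lower bound 46.7%, pass.
- 78/144 = 54.2%: lower bound 46.0%, fail.
- P(X ≥ 79 | n = 144, p = 0.588) = 85.2%, exact binomial.

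**Step 5: effect of counting rupture as failure.** Only ruptures in subjects who would otherwise be successes matter. The documents give no rate, so the counts are assumptions. Each such subject lowers the expected rate by 1/144 = 0.7 points.

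| Otherwise-successful ruptures (assumed) | Expected rate | P(X ≥ 79) |
|---|---|---|
| 0 | 58.8% | 85% |
| 1 | 58.1% | 81% |
| 2 | 57.4% | 76% |

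The planned analysis uses Rubin's combined variance, so the 79-of-144 boundary approximates the actual decision rule and does not reproduce it exactly.

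**The case against.** The best defence is that the design is coherent. Anatomy carries effectiveness, clinical harm carries safety, and both must be met for study success. Section 1.1 names exclusion of the lesion from the circulation as the way to prevent bleeding, and complete occlusion measures that. It does not say that rupture must be part of the endpoint. Rupture is also not hidden. Hemorrhagic stroke is within the stroke definition, neurological and serious events are reportable (8.1.1), the CEC reviews reportable events (8.5), the DMC assesses reported events (8.6), and rupture has its own endpoint at 1, 3 and 5 years. All of that stands, and it limits the weight of the point.

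It does not close the gap. Effectiveness is not purely anatomical, because retreatment already fails a subject whatever the image shows. Reporting rupture elsewhere also does not stop a subject with a fatal rupture from being imputed as occluded.

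A second objection is that 46.3% is a complete-occlusion rate, so adding rupture makes the comparison less like-for-like. The sponsor already applies that goal to an endpoint with retreatment and stenosis failures added. One more failure component can only make the test stricter. The sponsor should still confirm that the goal fits.

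A reader might infer that a rupture counts against the device only if it kills or causes a major stroke. The documents do not support this. Retreatment after rupture, or Raymond II or III at 1 year, fails effectiveness whatever the NIHSS.

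**Conclusion.** The point holds in this form: rupture is not a failure criterion in its own right in either primary endpoint. One course after rupture is scored as success on both, and a rupture without a 1-year image or retreatment, fatal or not, goes to imputation for effectiveness.

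The size cannot be determined from the documents. The number of affected subjects may be zero. With one or two, the chance of passing would be about 81% or 76% instead of 85%, given 144 complete subjects, a true rate of 58.8% under the current definition, and no allowance for imputation variance. The case therefore rests on the meaning of the endpoint, not on an expected loss of power. It is a cheap improvement and does not by itself undermine the study.

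**What to change.** In 3.2.2, 10.1.1 and 10.3.4, add: *Any rupture of the target aneurysm after the end of the index procedure and up to the 1-year assessment is a failure on the primary effectiveness endpoint and is not imputed.* The effectiveness wording in the Protocol Summary should match.

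Name one source for rupture. CEC adjudication of reported hemorrhage, supported by imaging, is the natural choice, because the events are already reportable and CEC-reviewed. Sections 3.2.4, 10.1.3 and 10.3.6 now assign rupture to the core laboratory, although the list of core-laboratory evaluations in 6.2.3 does not include it. They need to be made consistent with the chosen source, and the CEC charter should name the event.

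Reconcile the major-stroke threshold between the Protocol Summary, 3.2.1 and 10.1.1.

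The cost is one clause and consistent cross-references, with no new visits or imaging. The test becomes slightly stricter, by 0.7 points of observed rate for each otherwise-successful rupture at n = 144, and the sponsor should confirm that 46.3% remains a suitable goal for the revised definition.

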6.2.3. Core Laboratory for Image Evaluation

An independent radiographic core laboratory shall be utilized to provide an unbiased and standardized assessment of all imaging. All subject PHI will be removed before an image is uploaded and evaluated. The core lab assessor will be blinded to subjects' previous medical history. The core lab will evaluate the following:

- Aneurysm and vessel dimensions
- Ability to retain embolic coils without coil protrusion/herniation (yes/no)
- Aneurysm occlusion: evaluated per the Raymond– Roy scale referenced in Section 3.2.2
- Parent and branch vessel stenosis: evaluated on a scale of 0-50% and > 50-100%
- Device migration: migration is defined as > 2mm

All imaging shall be performed in accordance to the core laboratory recommended protocol provided to the sites. A copy of the study angiograms will be submitted to the core lab.

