7.4. Procedure Assessments

Index procedure start/end times will be recorded and the following definitions apply to the index procedure:

- Procedure start time is defined as the point when the guiding catheter is introduced into the subject.
- Procedure end time is defined as the time the last catheter is removed from the subject.

Procedural assessments – pre-treatment, intra-treatment and post-treatment include:

- Procedural medications
- Event assessment
 - Adverse events
 - Protocol deviations
 - Device malfunctions/deficiency
 - Angiogram
 - Post-treatment aneurysm occlusion per Raymond– Roy scale
 - Send the pre-treatment, intra-procedure, and post-treatment DSA to the core lab

At a minimum, the following data will also be captured during the procedure:

- Name of the implanting physician
- Aneurysm and vessel dimensions
- PulseRider device implanted
- Device implant success
- Adjunctive devices used including coils and balloons
- Ancillary devices used including the microcatheter
- Fluoroscopy time

- Presence of vasospasm (vessel and times of onset/resolution). Vasospasm will be captured as an adverse event only if it leads to a subsequent thrombotic or ischemic event.

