7.11. Retreatment

At the discretion of the investigator, a subject who has received a PulseRider device may be retreated (e.g. with coils, stent, etc.) at any time. All subjects who are retreated will remain in the study and will continue to receive all follow-up assessments based on the date of the index procedure per the Schedule of Assessments in Section 7.15. When a subject returns for a retreatment, this is considered an unscheduled visit and the evaluations noted for unscheduled visits must be completed. Data from the retreatment procedure will be captured in the appropriate eCRF, and data from the remaining unscheduled assessments will also be captured in the eCRFs. No pre-planned staged procedures on target aneurysms will be allowed in the study.

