10.1.2. Secondary Endpoints

- Technical Success is defined as successful implantation of device— physician able to access target aneurysm, deploy PulseRider device at the neck of aneurysm and device was detached successfully. This endpoint will be reported by the investigator. The following hypothesis test of this endpoint will be performed if the primary safety and effectiveness endpoint null hypotheses are both rejected:
 - Null hypothesis H_0 : $p_{\text{TechnicalSuccess}} \leq \text{PG of } 79\%$
 - Alternative hypothesis H_A : $p_{\text{TechnicalSuccess}} > \text{PG of } 79\%$
 - Where $p_{\text{TechnicalSuccess}}$ is the rate of technical success
 - Decision Criterion: The decision will be made to reject the null hypotheses and conclude the alternative hypothesis if the lower bound of a two-sided 95% normal approximation based confidence interval is $> \text{PG of } 79\%$. With 160 subjects, a rate for technical success of at least 85% is required to demonstrate success on this endpoint.
- Ability to retain embolic coils within aneurysm immediately post-procedure (as evaluated by the core lab)
- Complete aneurysm occlusion at 3 years and 5 years. Complete aneurysm occlusion is defined as Raymond I. Aneurysm occlusion grading will be evaluated by the independent core laboratory.
- Adequate aneurysm occlusion (defined as Raymond I and II combined) at 1 year, 3 years and at 5 years. Aneurysm occlusion grading will be evaluated by the independent core laboratory.
- The percentage of target aneurysms that are retreated through 1 year, 3 years and 5 years. Retreatment will be reported by the investigator.

- The percentage of subjects with significant stenosis defined as $> 50\%$ at implant site at 1 year, 3 years and 5 years. This endpoint will be evaluated by the independent core laboratory
- The percentage of subjects with mRS 0 – 2 at 1 year, 3 years and 5 years

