10.3.5. Secondary Endpoint Analyses

The analysis of technical success which is reported by the investigator will be conducted on the mITT analysis set. The endpoint will be considered successful if the lower bound of the 2-sided 95% normal approximation based confidence interval for the rate is greater than a performance goal of 79%.

The analyses of the remaining secondary effectiveness endpoints listed below will be conducted on the PP analysis set using the observed data.

- The ability to retain embolic coils within aneurysm immediately post-procedure as reported by the independent core laboratory
- Complete aneurysm occlusion at 3 years and 5 years as reported by the independent core laboratory
- Adequate aneurysm occlusion at 1 year, at 3 years and 5 years as reported by the independent core laboratory
- The percentage of target aneurysms that are retreated through the 1 year, 3 year and 5 year as reported by the investigator
- The percentage of subjects with significant stenosis defined as > 50% at implant site at 1 year, 3 years and 5 years as reported by the independent core laboratory
- The percentage of subjects with mRS 0-2 at 1 year, 3 years and 5 years

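### A stent or other non-coil implant added to a detached PulseRider in the index session is most naturally read as not being retreatment, so occlusion at 1 year is credited to PulseRider with coils

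*Combined protocol and SAP*

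**What the plan says.** - **Primary effectiveness (3.2.2, 10.1.1, 10.3.4).** "Success on this endpoint is defined as complete aneurysm occlusion (Raymond I) without retreatment or significant parent artery stenosis", assessed at 1 year. Section 3.2.2 adds: "Retreatment will be reported by the site".
- **Analysis set (10.1.6, 10.3.4).** The primary effectiveness analysis uses the PP set. PP requires successful PulseRider implantation and no major deviation on eligibility or dual antiplatelet therapy. An additional implant does not exclude a subject.
- **Retreatment (7.11).** There is no formal definition. The section says that "a subject who has received a PulseRider device may be retreated (e.g. with coils, stent, etc.) at any time", and then: "When a subject returns for a retreatment, this is considered an unscheduled visit".
- **Index-procedure devices (7.4).** The data to be captured include "Adjunctive devices used including coils and balloons". No endpoint consequence is attached.
- **Technical success (3.2.3, 10.1.2, 10.3.5).** The physician must access the aneurysm, "deploy PulseRider device at the neck of aneurysm and device was detached successfully". There is no condition about other implants. "The analysis of technical success which is reported by the investigator will be conducted on the mITT analysis set".
- **Coil retention (3.2.3, 6.2.3).** The core laboratory reads it as yes or no, immediately post-procedure, with absence of protrusion or herniation as part of the item.
- **Elsewhere.** Section 6.4 deals only with other aneurysms. The sensitivity analyses in 10.3.10 deal only with missing data.

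**The concern.** The primary question is whether PulseRider with coils exceeds 46.3% complete occlusion. If coils do not stay in place behind a detached PulseRider and a stent is added before the session ends, closure at 1 year is the result of PulseRider, coils and stent together. On the natural reading of the plan, that subject counts as a success for PulseRider with coils. Had the same stent been placed at a later visit, the subject would be a failure. Two subjects with the same need for a second device would then be scored in opposite ways according to timing alone.

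The plan itself foresees the situation. Table 1.5.1A lists coil prolapse or herniation through or around the device as a risk, and section 1.2 describes a stent across the neck as a way of preventing coil prolapse. Because sites report retreatment, they could also classify identical cases differently. What is at stake is the numerator of the primary effectiveness endpoint and, possibly, the coil-retention endpoint.

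**Working it through.** **1. How each case is scored**

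| Case | PP set | Technical success | Raymond I at 1 year (no significant stenosis) |
|---|---|---|---|
| PulseRider detached, coils only | In | Yes | Success |
| PulseRider detached, stent added in the same session | In | Yes | Success on the natural reading |
| PulseRider detached, stent added at a later visit | In | Yes | Failure (retreatment) |
| PulseRider not implantable, other implant used instead | Out | No (failure in mITT) | Not counted |

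Only the second row is open to question.

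**2. The plan's own figure**

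Inputs from 10.2: 160 subjects, 10% attrition, expected rate 58.8%, goal 46.3%. The interval is two-sided 95% normal-approximation (10.3.4). Evaluable n = 160 × 0.90 = 144.

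- Normal approximation with null variance: Φ[(0.125 − 1.96 × √(0.463 × 0.537/144)) / √(0.588 × 0.412/144)] = 85.6%.
- Exact binomial power of the planned rule: 85.2%.

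Both agree with the stated 85%. This treats the 144 as the PP set with complete data and leaves out the multiple imputation.

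**3. Margin to the threshold**

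Lower bound = p̂ − 1.96 × √(p̂(1 − p̂)/144).

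- 78/144: 46.0%, fails.
- 79/144: 46.7%, passes.
- Expected successes: 0.588 × 144 = 84.7, about 85.

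Rescoring 85 − 78 = 7 successes as failures (7/144 = 4.9%) turns a pass into a fail. If added-implant subjects occlude at 58.8%, 7 such successes correspond to about 7/0.588 = 12 subjects, or 12/144 = 8.3%.

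**4. Chance of passing when the true rate is at the goal**

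The documents give no rate of added implants, so r = 2%, 5% and 10% are assumptions. The chance is the exact binomial P(X ≥ 79) with n = 144. It depends on what the 46.3% is taken to mean:

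- **Model A.** 46.3% is the rate with added-implant subjects scored as failures, and those subjects occlude at 58.8%. Counted rate = 0.463 + 0.588r.
- **Model B.** As A, but they occlude at the same rate as everyone else. Counted rate = 0.463/(1 − r).
- **Model C.** 46.3% is the rate among subjects without an added implant, and the others occlude at 58.8%. Counted rate = 0.463(1 − r) + 0.588r.

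| r | A | B | C |
|---|---|---|---|
| 0% | 2.4% | 2.4% | 2.4% |
| 2% | 4.5% | 4.0% | 2.8% |
| 5% | 10.3% | 8.3% | 3.4% |
| 10% | 28.8% | 23.1% | 4.7% |

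**5. Power if these subjects are scored as failures**

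With 58.8% occlusion in all subjects, the counted rate becomes 0.588(1 − r). Exact power falls from 85.2% to about 78%, 63% and 35% at r = 2%, 5% and 10%.

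**The case against.** **The plan is silent rather than explicit.** This stands. Section 7.11 allows retreatment at any time, and its sentence about a returning subject may say only how a return is logged. Section 10.3.4 also uses the word retreatment, under the safety endpoint, for subjects whose implantation failed, with no return-visit limit. A reader might infer that the plan exempts same-session implants. It does not say so; that is only the most natural reading.

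**Not every rescue implant escapes.** A reader might infer that any bail-out device avoids failure on every effectiveness endpoint. It does not: when another implant replaces a PulseRider that could not be implanted, the subject fails technical success and leaves PP.

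**Other documents may settle it.** Section 10 announces a separate SAP with more detail on derivations, and the device is used under the IDE instructions for use. Neither is available here, so it cannot be said that added implants are permitted without limit. The endpoint text is nevertheless where the scoring rule belongs.

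**Coil-retention bias is not established.** The image is read after the procedure, possibly with a stent already in place. But the item requires absence of protrusion or herniation, and nothing shows how the core laboratory would read herniated coils held by a stent.

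**The benchmark may have counted adjunct implants as successes.** Section 10.1.1 names X/Y stenting as a comparator only for the safety goal. For effectiveness it names clipping and endovascular treatment, without saying how same-session adjuncts were scored. Scoring them as failures could make the endpoint stricter than its benchmark. This stands, and is the reason for the sensitivity analysis proposed below.

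**The largest probabilities come from one model.** Also true: under model C the inflation is small.

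**Conclusion.** The concern holds for one class of subject: PulseRider detached, with another non-coil permanent implant added at the target aneurysm in the same session. For these subjects the success rule, on its most natural reading, credits a combined result to PulseRider with coils, and scores the same implant differently according to when it is placed. The classification is left to the site.

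The size is uncertain because no rate of added implants is given. The firm figure is the margin: 79 successes needed against about 85 expected, so 7 rescored successes reverse the conclusion. With the true rate at the goal, the chance of passing rises from 2.4% to 2.8–4.5%, 3.4–10.3% and 4.7–28.8% for assumed rates of 2%, 5% and 10%. The upper ends require model A and should not be quoted alone. An effect on coil retention is possible but not shown.

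The rule should be settled before outcomes are known, because the data needed to apply it are already to be collected.

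**What to change.** This changes scoring only; treatment decisions stay with the physician.

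1. In 3.2.2, 10.1.1 and 10.3.4, state that a non-coil permanent implant added to a detached PulseRider at the index procedure, to support coils or treat the target aneurysm, is scored as a primary effectiveness failure, as later retreatment is. Limiting the rule to that purpose keeps out implants placed for unrelated reasons, such as a vessel dissection.
2. In 10.3.10, add a sensitivity analysis of the primary endpoint with these subjects scored by their imaging result.
3. Report coil retention and technical success with and without these subjects.
4. List such implants explicitly in the adjunctive-device item of the eCRF.

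The cost is a few sentences and an eCRF pick-list, since section 7.4 already captures adjunctive devices. The reported success rate and the effective power may fall. The loss is modest if added implants are rare (about 78% power at 2%) but substantial if they are not (about 63% at 5%), so the sponsor should state an expected rate and check the sample size against it.
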